Hypothyroidism	2-4	Therapy with pembrolizumab can be continued while treatment for the thyroid disorder is instituted	Therapy with pembrolizumab can be continued while treatment for the thyroid disorder is instituted
Myocarditis	Grade 1 or 2	Withhold	Based on severity of AE administer corticosteroids
	Grade 3 or 4	Permanently discontinue	
All other immune-related AEs	Intolerable/ Persistent Grade 2	Withhold	Based on type and severity of AE administer corticosteroids
Infusion reaction	3-4	Permanently discontinue	Permanently discontinue
Pneumonitis	2	Hold until toxicity resolves to Grade 0-1	If toxicity does not resolve within 12 weeks of last dose or inability to reduce corticosteroid to 10 mg or less of prednisone or equivalent per day within 12 weeks
	3-4	Permanently discontinue	Permanently discontinue
Renal failure or nephritis	2	Hold until toxicity resolves to Grade 0-1	If toxicity does not resolve within 12 weeks of last dose or inability to reduce corticosteroid to 10 mg or less of prednisone or equivalent per day within 12 weeks

Proprietary and Confidential

The information in this document is considered privileged and confidential, and may not be disclosed to others except to the extent necessary to obtain Institutional Review Board approval and informed consent, or as required by federal and state laws. Persons to whom this information is disclosed should be informed that this information is privileged and confidential and that it should not be further disclosed.

Toxicity	Hold Treatment For Grade	Timing for Restarting* Treatment	Discontinue Subject
	3-4	Permanently discontinue	Permanently discontinue
All other drug-related toxicity ³ attributed to pembrolizumab	3 or severe 2	Hold until toxicity resolves to Grade 0-1 or baseline grade if abnormal at baseline	If toxicity does not resolve within 12 weeks of last dose or inability to reduce corticosteroid to 10 mg or less of prednisone or equivalent per day within 12 weeks
	4	Permanently discontinue	Permanently discontinue

Note: Permanently discontinue for any severe AE that recurs or any life-threatening event.

* Dose interruptions or delays in start of a cycle for any reason (toxicity or non-toxicity) during Induction Phase (Cycles 1 and 2 in Efficacy Cohort (Part 2), Cycles 2 and 3 in Safety and Expansion Cohorts (Parts 1 and 3)) should be applied to both GM-CSF and pembrolizumab together so that both drugs are restarted on Day 1 of each cycle.

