¹ For patients with liver metastasis who begin treatment with Grade 2 AST or ALT, treatment is not required to be held for Grade 2 AST or ALT.

² For patients with baseline Grade 2 AST or ALT, Grade 3 AST or ALT does not automatically require treatment discontinuation. If AST or ALT increases by greater than or equal to 50% relative to baseline and is assessed as treatment-related (e.g. no evidence of interval tumor progression or biliary obstruction) and lasts for at least 1 week despite supportive care, then patients should be discontinued.

³ Patients with intolerable or persistent Grade <3 drug-related AE may hold study medication at physician discretion. Permanently discontinue study drug for persistent Grade 2 adverse reactions for which treatment with study drug has been held, that do not recover to Grade 0-1 within 12 weeks of the last dose. Patients with mild grade 3 toxicity (e.g. mild or asymptomatic rashes or asymptomatic laboratory abnormalities) may be continue on treatment with augmented supportive care and close monitoring at discretion of treating physician.

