5.5.2 Prohibited Concomitant Medications

Subjects are prohibited from receiving the following therapies during the Screening and Treatment Phase (including retreatment for post-complete response relapse) of this trial:

- Antineoplastic systemic chemotherapy or biological therapy

- Immunotherapy not specified in this protocol
- Chemotherapy not specified in this protocol
- Investigational agents other than pembrolizumab and GM-CSF
- Radiation therapy
- Live vaccines within 30 days prior to the first dose of trial treatment and while participating in the trial.
 - Examples of live vaccines include, but are not limited to, the following: measles, mumps, rubella, varicella/zoster, yellow fever, rabies, BCG, and typhoid vaccine.
- Systemic glucocorticoids for any purpose other than to modulate symptoms from a suspected immune-related AE (irAE) or as premedication for iodinated contrast if not amenable to MRI imaging instead of contrast CT. The use of physiologic/replacement doses of corticosteroids may be approved after consultation with the Study Chair.
- Antiviral therapy for active HCV is not allowed during protocol therapy unless approved by the Study Chair due to unknown potential for toxicity in combination.

Subjects who, in the assessment by the investigator, require the use of any of the aforementioned treatments for clinical management should be removed from the trial. Subjects may receive other medications that the investigator deems to be medically necessary.

The Exclusion Criteria section 5.1.3 describes other medications which are prohibited in this trial.

There are no prohibited therapies during the Post-Treatment Follow-up Phase.

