5.6 Rescue Medications & Supportive Care

5.6.1 Supportive Care Guidelines for Pembrolizumab

Subjects should receive appropriate supportive care measures as deemed necessary by the treating investigator. Suggested supportive care measures for the management of adverse events with potential immunologic etiology are outlined below and in greater detail in the ECI guidance document. Where appropriate, these guidelines include the use of oral or intravenous treatment with corticosteroids as well as additional anti-inflammatory agents if symptoms do not improve with administration of corticosteroids. Note that several courses of steroid tapering may be necessary as symptoms may worsen when the steroid dose is decreased. For each disorder, attempts should be made to rule out other causes such as metastatic disease or bacterial or viral infection, which might require additional supportive care. The treatment guidelines are intended to be applied when the investigator determines the events to be related to pembrolizumab.

If after the evaluation the event is determined not to be related, the investigator is instructed to follow the ECI reporting guidance but does not need to follow the treatment guidance (as outlined in the ECI guidance document). Refer to Section 5.2.2.1 for guidance on pembrolizumab dose modifications.

Suggested steroid regimens include:

- Systemic steroids equivalent to prednisone 1-2 mg/kg/day for severe immune-related toxicity requiring immunosuppressive therapy.
- Oral prednisone 0.5 mg/kg/day or other equivalent steroid regimen for mild-moderate immune-related toxicity requiring immunosuppressive therapy.
- Topical corticosteroids for mild-moderate dermatitis.
- Corticosteroid eye drops for ocular immune-related toxicity.
- Once symptoms resolve or return to Grade 1/baseline, initiate slow steroid taper over at least 4 weeks, with close monitoring.

It may be necessary to perform conditional procedures such as bronchoscopy, endoscopy, or skin photography as part of evaluation of the event. Suggested conditional procedures, as appropriate, can be found in the ECI guidance document.

- **Pneumonitis:**

- For **Grade 2 events**, treat with systemic corticosteroids. When symptoms improve to Grade 1 or less, steroid taper should be started and continued over no less than 4 weeks.
- For **Grade 3-4 events**, immediately treat with intravenous steroids. Administer additional anti-inflammatory measures, as needed.

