 - **Grade 2** hyperthyroidism events (and **Grade 2-4** hypothyroidism):
 - In hyperthyroidism, non-selective beta-blockers (e.g. propranolol) are suggested as initial therapy.
 - In hypothyroidism, thyroid hormone replacement therapy, with levothyroxine or liothyroinine, is indicated per standard of care.
 - **Grade 3-4** hyperthyroidism events: Treat with an initial dose of IV corticosteroid followed by oral corticosteroids. When symptoms improve to Grade 1 or less, steroid taper should be started and continued over no less than 4 weeks. Replacement of appropriate hormones may be required as the steroid dose is tapered.
- **Hepatitis attributed to immune toxicity:** Assessment should be based upon greatest increase in AST, ALT, or total bilirubin. Elevations in alkaline phosphatase alone should not be used to determine treatment-related toxicity grade or supportive care interventions since this marker is commonly elevated in biliary tract cancers and may be an index of biliary obstruction independent of treatment-related toxicity. Evaluation for viral reactivation and antiviral therapy for HBV or HCV should be considered if any evidence hepatotoxicity according to standard institutional practice in HBV/HCV patients receiving anti-cancer therapies
 - For **Grade 2** events (if normal or Grade 1 at baseline), monitor liver function tests more frequently until returned to baseline values (consider weekly) to ensure not progressive.

- For **Grade 4** events and **Grade 3** if increased by greater than or equal to 50% relative to baseline and is assessed as treatment-related (e.g. no evidence of interval tumor progression or biliary obstruction), treat with intravenous corticosteroids for 24 to 48 hours.
- When symptoms improve to Grade 0-1 or baseline, a steroid taper should be started and continued over no less than 4 weeks.
- **Renal failure or Nephritis:**
 - For **Grade 2** events assessed as treatment-related and despite best supportive care (e.g. oral or IV hydration), treat with oral or systemic corticosteroids.
 - For **Grade 3-4** events, treat with systemic corticosteroids.
 - When creatinine value improves to Grade 1 or less, steroid taper should be started and continued over no less than 4 weeks.
- **Other immune-mediated adverse reactions, including ocular manifestations**
 - Permanently discontinue pembrolizumab if clinically significant or severe immune-mediated adverse reactions (see 5.2.2.1).

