 - Initiate systemic corticosteroids at a dose of 1 to 2 mg/kg/day prednisone or equivalent for severe immune-mediated adverse reactions.
 - Administer corticosteroid eye drops to patients who develop uveitis, iritis, or episcleritis. Permanently discontinue ipilimumab for immune-mediated ocular disease that is unresponsive to local immunosuppressive therapy.
- **Infusion reactions:** Signs and symptoms usually develop during or shortly after drug infusion and generally resolve completely within 24 hours of completion of infusion.

Table 4 below shows treatment guidelines for subjects who experience an infusion reaction associated with administration of pembrolizumab (MK-3475).

Table 4 Infusion Reaction Treatment Guidelines

NCI CTCAE Grade	Treatment	Premedication at subsequent dosing
Grade 1 Mild reaction; infusion interruption not indicated; intervention not indicated	Increase monitoring of vital signs as medically indicated until the subject is deemed medically stable in the opinion of the investigator.	None
Grade 2 Requires infusion interruption but responds promptly to symptomatic treatment (e.g., antihistamines, NSAIDS, narcotics, IV fluids); prophylactic medications indicated for <=24 hrs	Stop Infusion and monitor symptoms. Additional appropriate medical therapy may include but is not limited to: IV fluids Antihistamines NSAIDS Acetaminophen Narcotics	Subject may be premedicated 1.5h (\pm 30 minutes) prior to infusion of pembrolizumab (MK-3475) with: Diphenhydramine 50 mg po (or equivalent dose of antihistamine). Acetaminophen 500-1000 mg po (or equivalent dose of antipyretic).

NCI CTCAE Grade	Treatment	Premedication at subsequent dosing
	
Increase monitoring of vital signs as medically indicated until the subject is deemed medically stable in the opinion of the investigator. If symptoms resolve within one hour of stopping drug infusion, the infusion may be restarted at 50% of the original infusion rate (e.g., from 100 mL/hr to 50 mL/hr). Otherwise dosing will be held until symptoms resolve and the subject should be premedicated for the next scheduled dose.
 
Subjects who develop Grade 2 toxicity despite adequate premedication should be permanently discontinued from further trial treatment administration.
	

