7.2 Assessing and Recording Adverse Events

An adverse event is defined as any untoward medical occurrence in a patient or clinical investigation subject administered a pharmaceutical product and which does not necessarily have to have a causal relationship with this treatment. An adverse event can therefore be any unfavorable and unintended sign (including an abnormal laboratory finding, for example), symptom, or disease temporally associated with the use of a medicinal product or protocol-specified procedure, whether or not considered related to the medicinal product or protocol-specified procedure. Any worsening (i.e., any clinically significant adverse change in frequency and/or intensity) of a preexisting

condition that is temporally associated with the use of the investigational product(s), is also an adverse event. Adverse events may occur during the course of the use of the investigational products during the Treatment Period or within the Follow-Up Phase of this study. Progression of the cancer under study is not considered an adverse event unless it is considered to be drug related by the investigator.

The investigational products in this study are pembrolizumab and GM-CSF.

All adverse events will be recorded from the time the consent form is signed through 30 days following cessation of treatment and at each examination on the Adverse Event case report forms/worksheets. The reporting timeframe for adverse events meeting any serious criteria is described in section 7.2.3.

7.2.1 Definition of an Overdose for This Protocol and Reporting of Overdose to the Study Chair and to Merck

For purposes of this trial, an overdose of pembrolizumab will be defined as any dose of 1,000 mg or greater or GM-CSF 1250 µg or greater in a single dose (≥ 5 times the indicated dose). No specific information is available on the treatment of overdose of pembrolizumab. Appropriate supportive treatment should be provided if clinically indicated. In the event of overdose, the subject should be observed closely for signs of toxicity. Appropriate supportive treatment should be provided if clinically indicated.

If an adverse event(s) is associated with (“results from”) the overdose of a Merck product, the adverse event(s) is reported as a serious adverse event, even if no other seriousness criteria are met.

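### The ocular stop instruction in section 5.6.1 names ipilimumab, which is not a study drug; other rules cover most cases, leaving a narrow gap for non-severe disease that recovers within 12 weeks

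*Combined protocol and SAP*

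**What the plan says.** The sentence stands in section 5.6.1, in the bullets on other immune-mediated reactions including ocular ones. It follows the advice to give corticosteroid eye drops for uveitis, iritis or episcleritis, and reads: "Permanently discontinue ipilimumab for immune-mediated ocular disease that is unresponsive to local immunosuppressive therapy".

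The rest of the protocol is clear about what is given. Section 7.2 states: "The investigational products in this study are pembrolizumab and GM-CSF". Table 2 in section 5.2.1 lists the same two drugs and no other. Section 5.5.2 prohibits, among other things, "Immunotherapy not specified in this protocol". The scope of section 5.6.1 is also stated: "The treatment guidelines are intended to be applied when the investigator determines the events to be related to pembrolizumab".

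Several other rules bear on the same patients:

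- Section 5.6.1, first bullet under the same heading: pembrolizumab is stopped permanently for immune-mediated reactions that are clinically significant or severe, with a pointer to section 5.2.2.1.
- Section 5.2.2.1, text before Table 3: withholding pembrolizumab according to the table is mandatory.
- Table 3, row "All other immune-related AEs": withhold for intolerable or persistent Grade 2, and give corticosteroids according to type and severity.
- Table 3, catch-all row for other drug-related toxicity: for Grade 3 or severe Grade 2, "Hold until toxicity resolves to Grade 0-1 or baseline grade if abnormal at baseline", with discontinuation if unresolved at 12 weeks; permanent stop for Grade 4.
- Table 3, footnote 3: permanent discontinuation for persistent Grade 2 reactions for which drug was held and "that do not recover to Grade 0-1 within 12 weeks of the last dose".

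**The concern.** This is current safety text, and the action it orders is the strongest available: permanent discontinuation. It attaches that action to a drug that no subject is assigned and that the prohibited-medication list excludes. A reader who follows the words exactly stops nothing.

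The trigger differs from those around it. The neighbouring bullet turns on whether the reaction is judged clinically significant or severe. This sentence turns on failure of local therapy, with no grade attached. Table 3 has no ocular row that would carry that trigger in its place. At stake is whether a subject whose eye disease did not respond to drops should be taken off pembrolizumab for good, or held and possibly restarted.

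**Working it through.** No arithmetic applies. The check has two parts.

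**1. Is the named drug a study drug?** Table 2 and section 7.2 each give two products, pembrolizumab and GM-CSF; the sentence names neither. Ipilimumab's other appearances are background on approvals and earlier combinations (sections 4.2.1, 4.3.3 and 4.3.4), benchmark toxicity rates (sections 4.3.6.3 and 8.4.4) and the reference list. None makes it part of the treatment.

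**2. What would happen to pembrolizumab without the sentence?** Take ocular disease that has failed local immunosuppression and sort it by severity. Table 6 in section 7.2.4 defines Grade 1 as needing no intervention and Grade 2 as needing minimal, local or noninvasive intervention. On those general definitions, disease that needed eye drops is at least Grade 2.

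| Situation | Rule that applies now | Outcome now | Outcome if the sentence named pembrolizumab |
|---|---|---|---|
| Grade 4 or life-threatening | Table 3 catch-all row and note | Permanent stop | Permanent stop |
| Judged clinically significant or severe | 5.6.1, first bullet | Permanent stop | Permanent stop |
| Persistent Grade 2, not so judged; held, not recovered by 12 weeks | Table 3 immune-related row, then footnote 3 | Hold, then permanent stop | Permanent stop at once |
| Persistent Grade 2, not so judged; held, recovered within 12 weeks | Table 3 immune-related row | Hold; nothing directs a permanent stop, so restart is possible | Permanent stop at once |

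The first two rows do not differ. The third differs only in timing, because drug is withheld in the interval. The fourth is the one place where the outcome differs: a possible rechallenge against a permanent stop.

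Two further provisions do not close that row. Section 5.2.2 permits discontinuation for any toxicity the investigator considers a risk to the patient. Section 5.8 requires it for unacceptable adverse experiences or when the investigator decides to withdraw the subject. Either could lead to a stop, but neither makes failure of local therapy the trigger.

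One point of reading: the marker for footnote 3 sits on the catch-all row for drug-related toxicity, not on the immune-related row. Its sentence is worded generally, for any held Grade 2 reaction, and it is read that way here.

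**The case against.** The strongest reply is that nobody would be misled. The section is titled for pembrolizumab and limited to events related to it, and the bullet above names the right drug. Section 5.6.1 describes its measures as suggested and sends the reader to section 5.2.2.1 for dose modification. It also relies on a separate guidance document on events of clinical interest, not supplied here, which may carry the correct wording. Many clinicians would call eye disease that fails local immunosuppression clinically significant, and the first bullet then applies. Most of this stands, and it is why the point is minor. It does not remove the error: a permanent-stop instruction should not depend on the reader supplying the drug name, and the missing guidance document cannot be assumed to repair it.

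A second reply concerns the remedy. The documents do not show whether an immediate stop was intended for pembrolizumab, or whether the sentence was carried over and should give way to Table 3. Putting in the right name without touching Table 3 would leave one section ordering a permanent stop where the other orders a hold. That stands, and the fix allows for it.

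On the other side, a reader might infer that refractory ocular disease is left wholly to the investigator's judgment. The documents do not support that: withholding under Table 3 is mandatory, and footnote 3 makes the stop permanent at 12 weeks without recovery.

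**Conclusion.** The error is certain and its consequence is small. Read literally, the sentence stops neither of the two study drugs. The only change in outcome is for non-severe ocular disease that fails local therapy, is not judged clinically significant, and recovers within 12 weeks of the last dose. Such a subject could be rechallenged, where the corrected sentence would not allow it. This rests on reading footnote 3 as covering immune-related events and on the general grade definitions in Table 6.

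A reader might want a count of subjects affected. The documents report no ocular events and no incidence, so any figure would rest on an outside assumption, and none is offered. Nor can the issue be confined with certainty to the 15 Expansion Cohort subjects. The completed label on Stages 1 and 2 in the trial summary stands against subject numbers and the enrollment period, and does not show that treatment has ended.

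No endpoint, analysis population, sample-size figure or planned analysis is affected. The change is worth making when the protocol is next opened; it does not call for an amendment of its own.

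**What to change.** In section 5.6.1, replace ipilimumab with pembrolizumab in the ocular sentence, subject to confirmation by the sponsor's safety team that an immediate permanent stop is what they want. If they confirm it, add an ocular entry to Table 3, or a cross-reference from its immune-related row to section 5.6.1, so that the two sections give the same instruction. If they prefer hold-and-reassess, delete the sentence and let Table 3 govern.

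The cost is one word and one table line or cross-reference at the next amendment, plus a short confirmation from the safety team. Nothing in the statistical section needs to change.

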5.6.2 Supportive Care for GM-CSF

- **Edema:** Diuretics, dietary sodium restriction, limb elevation, compression stockings, and other standard supportive care interventions may be implemented according to standard of care at investigator discretion.
- **Injection site reactions:** Patients and/or caregivers will receive subcutaneous injection teaching each induction cycle, including instructions to avoid administering near waist or navel and to rotate injection sites.
- See Section 5.2.2.2 for guidance on dose modifications for toxicity attributed to GM-CSF.

5.6.3 General Supportive Care for Biliary Tract Cancer

- Antibiotics for cholangitis or stent/biliary drain prophylaxis: Antibiotics with biliary tract coverage may be administered at discretion of treating investigator for symptoms of cholangitis or prophylactically (such as before/after elective biliary drain or stent exchange or replacement).
- Antiviral therapy: Subjects with active HBV infection should receive appropriate antiviral therapy and close monitoring for reactivation according to institutional practice in patients

receiving potentially immunosuppressive anti-cancer therapies. Evaluation for viral reactivation and antiviral therapy for HBV or HCV should be considered if any evidence of hepatotoxicity according to standard institutional practice in HBV/HCV patients receiving anti-cancer therapies. Antiviral therapy for HCV is not permitted during protocol therapy unless approved by Study Chair.

- Diuretics: Diuretics such as furosemide and spironolactone may be used for the management of edema or ascites at the discretion of the treating physician. Severe episodes of edema, such as congestive heart failure, pleural effusion, ascites, pericardial effusion, or pulmonary edema may require additional measures such as percutaneous drainage, hospitalization, and/or discontinuation of protocol therapy.
- Electrolyte supplementation: Electrolytes should be repleted according to standard institutional protocols.
- Esophageal varices management: All patients with history of esophageal varices should be treated with optimal supportive care for this condition such as proton pump inhibitor and propranolol or other non-selective beta-blocker.
- Palliative radiation: Patients who require palliative radiation for worsening symptoms related to underlying malignancy must be removed from study. This may be considered a clinical progression event depending on judgment of treating investigator and clinical context.
- Supplements and alternative therapy: Treatment with non-conventional therapies (e.g., herbs or acupuncture), and vitamin/mineral supplements is acceptable provided that they do not interfere with treatment and the study endpoints and there is no known potential for drug interactions, according to assessment by the treating investigator and/or Investigational Pharmacist or designee.
- Topical agents: Topical steroid creams may be used to manage pruritic skin toxicity at the discretion of the treating physician. Non-alcohol-based topical emollients and non-alcohol-based moisturizers may be used for dry skin.
- Treatment of hypersensitivity or allergic reactions: Subjects who experience study drug-associated temperature elevations $\geq 38.5^{\circ}\text{C}$ or other hypersensitivity symptoms may be treated symptomatically with acetaminophen, steroids, diphenhydramine, meperidine, or other medications at the discretion of the treating investigator.

In addition, optimal standard of care therapies and best supportive care should be provided for other toxicity, comorbidity, or complications of biliary obstruction or liver disease which occur during protocol therapy, according to institutional standards.

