5.2.4 Trial Blinding/Masking

This is an open-label trial; therefore, the investigator and subject will know the treatment administered.

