followed for 30 days for adverse event monitoring (serious adverse events will be collected for 90 days after the end of treatment as described in Section 7.2.3.1). Subjects who discontinue for reasons other than progressive disease will have scheduled post-treatment follow-up monitoring for disease status until disease progression, initiating a non-study cancer treatment, withdrawing consent or becoming lost to follow-up. After documented disease progression each subject will be followed by chart review, clinic visits, or telephone contact for overall survival until death, withdrawal of consent, or the end of the study, whichever occurs first.

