8.3.2 Secondary Endpoints

- 1) **Safety** endpoint assessment is described in Section 7.2. The safety endpoints are AEs graded using CTCAE (Version 4.0) criteria. Safety will be assessed by quantifying the toxicities and grades experienced by subjects who have received pembrolizumab plus GM-CSF induction, including SAEs and ECIs. Other safety endpoints include laboratory safety assessments, ECOG performance status, Child Pugh score, vital signs, and physical examinations. The incidence and frequency of dose reduction, treatment delays, and discontinuation for lack of tolerability will be quantified. Re-induction and Second Course safety events will be addressed in the same manner.

- 2) **Tumor PD-L1 status** will be measured by IHC and classified as positive or negative by central laboratory testing (QualTek Laboratories) using pre-specified cut-points.
- 3) A key secondary endpoint is %PFS6 (formerly primary endpoint, changed by amendment with addition of Expansion Cohort). For each patient, PFS will be calculated in days and months from date of first dose of protocol therapy to date of first documented radiographic and/or clinical disease progression or death from any cause. For patients removed from study for other reasons than progression or death, PFS will be censored at the date last known to be progression-free. See Section 5.9 for Replacement policy for non-evaluable patients. The %PFS6 will be calculated as the proportion of evaluable patients progression-free at 6 months. Censored patients without progression will be treated as non-progression statistically and counted in denominator toward %PFS6.

For patients who continue on treatment despite radiographic progression based upon impression of clinical benefit an/or assessment with possible pseudo-progression or a delayed response⁴⁶ (see Section 5.8), PFS will be calculated at time of first documented progression after subsequent imaging confirms progression. If subsequent imaging does not demonstrate progression, then a PFS event will not have occurred and the patient will continue with scheduled imaging assessments per protocol to determine PFS.

Re-induction and Second Course PFS (rPFS, sPFS) will be calculated in months from date of first dose of re-induction or Second Course to date of first documented radiographic and/or clinical disease progression during or after re-induction or Second Course, or death from any cause. RPFS and sPFS will be reported descriptively.

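### Whether removal for palliative radiation counts as a PFS event is left to the open-label investigator without criteria, creating a risk of upward bias in PFS, DOR and %PFS6

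*Combined protocol and SAP*

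**What the plan says.** Section 5.6.3 (palliative radiation) first sets the removal rule: "Patients who require palliative radiation for worsening symptoms related to underlying malignancy must be removed from study". It then leaves the event status open: "This may be considered a clinical progression event depending on judgment of treating investigator and clinical context". No criteria follow. Section 5.2.4 confirms the setting: "This is an open-label trial; therefore, the investigator and subject will know the treatment administered".

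Section 8.3.2, item 3, ends PFS at the "date of first documented radiographic and/or clinical disease progression or death from any cause". For everyone else it says: "For patients removed from study for other reasons than progression or death, PFS will be censored at the date last known to be progression-free". For the six-month proportion it adds: "Censored patients without progression will be treated as non-progression statistically and counted in denominator toward %PFS6".

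On follow-up, Section 5.8 says that patients who stop for reasons other than progression "will have scheduled post-treatment follow-up monitoring for disease status until disease progression, initiating a non-study cancer treatment", among other stopping points. Section 7.1.6.4 continues imaging on similar terms. Sections 7.1.1.5.4 and 7.1.6.4.2 move patients to survival-only follow-up once a new anti-cancer therapy starts or care becomes palliative or end-of-life. None of these sections says how palliative radiation is classed.

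Section 4.3.6.2 says that locally assessed RECIST 1.1 determines progression, whereas 8.3.2 also admits clinical progression.

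**The concern.** By the wording of 5.6.3, the trigger is worsening of the cancer, not toxicity or logistics. That fits the clinical progression already admitted by 8.3.2, yet two investigators could score the same patient differently and both be within the protocol.

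If the removal is not called progression, the patient leaves the PFS analysis because the disease is getting worse. Censoring of that kind carries prognostic information, and Kaplan-Meier estimation assumes it does not. In %PFS6 the consequence is stronger: a patient removed at month 3, for example, is scored as progression-free at month 6. The DOR definition (8.3.2, item 4) also ends at progression or death and states no rule for these patients.

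There is no control arm to share the error. %PFS6 is compared with a fixed 20%, and OS and PFS are read against retrospective series. No independent review or sensitivity analysis is described for these cases.

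**Working it through.** **Inputs from the documents.** Section 8.6.2.3: n = 40 evaluable for PFS6, null 20%, alternative 40%, stated power 78% (2-sided 5%) and 87% (1-sided 5%). The scoring rules are those of 5.6.3 and 8.3.2.

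**Assumed.** The documents give no number or rate of palliative-radiation removals. I use k = 1 to 4 of 40 patients for the proportion, and a share q = 5%, 10% or 20% of events for Kaplan-Meier. The plan states no cut-offs, so I derive them.

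**Step 1: reproduce the plan's power.** Exact one-sample binomial, smallest cut-off c with P(X ≥ c | 40, 0.20) within the allowed tail:
- 1-sided 5%: c = 13, attained error 4.3%, power at 40% = 87.1% (stated 87%).
- 2-sided 5%, upper tail 2.5%: c = 14, attained error 1.9%, power 78.9% (stated 78%).

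Both agree to within one point, so 13 and 14 are reasonable working cut-offs.

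**Step 2: relabel k true failures in %PFS6.** Each adds 1/40 = 2.5 points. True successes are X ~ Bin(40, 0.20) and the reported count is X + k, so the false-positive rate is P(X ≥ c − k):

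| k | Points added | c = 13 | c = 14 |
|---|---|---|---|
| 0 | 0 | 4.3% | 1.9% |
| 1 | 2.5 | 8.8% | 4.3% |
| 2 | 5.0 | 16.1% | 8.8% |
| 3 | 7.5 | 26.8% | 16.1% |
| 4 | 10.0 | 40.7% | 26.8% |

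One patient roughly doubles the error at either cut-off. This works entirely through the 8.3.2 rule that scores censored patients as non-progression.

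**Step 3: Kaplan-Meier PFS.** For illustration take exponential PFS with a true six-month value of 20%: hazard λ = −ln(0.20)/6 = 0.268 per month, median ln 2/λ = 2.58 months. If a constant share q of events is replaced by censoring at the same time, Kaplan-Meier estimates a hazard of (1 − q)λ, so the six-month value is 0.20^(1 − q). The 8.3.2 proportion becomes 0.20 + 0.80q.

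| q | Kaplan-Meier at 6 months | Kaplan-Meier median (months) | Proportion under 8.3.2 |
|---|---|---|---|
| 5% | 21.7% | 2.72 | 24% |
| 10% | 23.5% | 2.87 | 28% |
| 20% | 27.6% | 3.23 | 36% |

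The direction is the same, but the effect is less than half as large in Kaplan-Meier as in the proportion.

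**The case against.** **Censoring is not automatic.** A reader might infer that every irradiated patient not called clinical progression drops out as censored. The documents do not support that. RECIST progression on a scan at or before removal is an event whatever the investigator says about the radiation, and scans come every 8 weeks ± 7 days in the first six months. Sections 5.8 and 7.1.6.4 also continue imaging after removal without progression. Whether radiation ends that imaging is unsettled: 5.5.2 lists it among prohibited treatments requiring removal, but separately from systemic antineoplastic therapy. This objection stands, so the point concerns patients with no documented RECIST progression.

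**Bias is not certain.** The same sentence lets the investigator call the event, and many may do so. This also stands. Relative to a rule that counts every such removal, however, discretion can only take events away.

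**The %PFS6 effect is not a separate flaw.** A reader might treat it as independent of how 8.3.2 handles censored patients. It is not: if patients censored before month 6 were scored as failures, the Step 2 inflation would vanish. What would remain is prognosis-related censoring in Kaplan-Meier PFS and the gap in DOR.

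**Size can be overstated.** Raising every patient's success probability to 22.5% or 25% gives 9.6% or 17.9% at a cut-off of 13, and 4.9% or 10.3% at 14. That is a different model from relabelling one or two patients, and its figures are too high for that scenario.

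**The remedy takes a side.** Symptomatic worsening at a radiographically stable lesion is not RECIST progression, and 4.3.6.2 points to RECIST alone. That conflict must be settled. A RECIST-only rule would remove the discretion but leave the prognosis-related censoring.

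**Consequence is limited.** These are secondary endpoints, and 8.6.2 calls for descriptive analysis of them. Even so, 8.6.2.3 gives %PFS6 its own hypotheses, test and power.

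**Conclusion.** The point holds as a risk. Event status after palliative radiation is undefined, and so is whether imaging continues. Where progression is not called and no RECIST progression is documented, the rules can score a patient failing before six months as a %PFS6 success.

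The firm figure is 2.5 points of %PFS6 per patient at n=40. The false-positive rates for one or two patients (8.8% or 16.1% against 4.3%; 4.3% or 8.8% against 1.9%) rest on an assumed count, a true rate of exactly 20% and derived cut-offs. The Kaplan-Meier figures are an exponential illustration. The documents do not show that such bias has occurred or how often these removals happen, and this point makes no claim about the primary endpoint, ORR. It is worth correcting before analysis because %PFS6 is a powered key secondary endpoint in an uncontrolled trial.

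**What to change.** In 8.3.2, with a cross-reference in 5.6.3, state that removal for palliative radiation because of worsening cancer-related symptoms is scored as a clinical progression event for PFS, %PFS6 and DOR. Date it at the decision to irradiate, unless RECIST progression was documented earlier. Report a sensitivity analysis that uses the investigator's call, with censoring where progression was not called.

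Reconcile 4.3.6.2 with 8.3.2 on whether progression is RECIST-only or also clinical, and state whether palliative radiation is a non-study cancer treatment for the purposes of disease-status follow-up.

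This changes endpoint scoring only, not patient care. It needs the removal reason and the decision date, a few sentences of text and one extra analysis run. The downside is that reported PFS may be slightly shorter.
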